6.3.1 Screening (Weeks -6 to -1)

Screening will begin up to 6 weeks before Day 0. During Screening, study information will be reviewed and discussed, and the participant will review and sign the informed consent form. No procedures, other than a preliminary verbal assessment of eligibility by review of inclusion/exclusion criteria, may be done before the informed consent process is complete. Once informed consent has been obtained and documented, the following Screening procedures may be completed:

- Record demographics, medical history (general and HIV), and the patient's height
- Record all prior ART exposure; record all other medications taken within the last 30 days
- Obtain documentation of HIV-1 infection; if official, signed, written documentation is unavailable, then collect a sample for HIV antibody testing as indicated below:
 - Obtain documentation of viral resistance, if available (within 6 months of Screening), and select an OBR
 - Record results of a complete physical examination
 - Record vital sign measurements
 - Record the patient's weight
 - Record only study-related AEs, which begin once the patient signs the informed consent (see Section 8.1 for definitions)
- Collect blood and urine for the following laboratory samples:
 - Hepatitis serology and C-reactive protein
 - Clinical laboratory assessments (serum chemistry, hematology, and urinalysis; see [Section 7.2.2](#) for a complete list of parameters)
 - Serum pregnancy test in females of childbearing potential and an FSH test in postmenopausal females
 - HIV-1 RNA (viral load)
 - HIV-1 antibody level, if documentation of HIV-1 infection is not provided as indicated above
 - HIV-1 viral resistance sample (will be stored for later use if needed)

- CD4⁺ cell count

If a patient fails Screening, they may be re-screened one time.

6.3.2 Day 0/Baseline

The Day 0/Baseline visit may take place at any point during the 4 weeks following the Screening Visit. At this visit, patients will receive the first study drug infusion: a loading dose of 2,000 mg. All patients must be observed for 1 hour after completion of study drug administration at Baseline. If the patient does not experience an AE(s) related to the infusion (local or systemic) through and including the second infusion on Day 14, then the observation time can be reduced to 15 minutes thereafter. Patients will return to the site every 2 weeks (± 2 days) for the remainder of the study to receive additional study drug and for effectiveness and safety evaluations. At this visit, the following will be completed before study drug administration:

- Record any changes to ART; record all other medications taken within the 30 days before the baseline visit
- Record results of a complete physical examination
- Record vital sign measurements
- Record the patient's weight
- Record only study-related AEs
- Collect blood and urine samples for the following:
 - Clinical laboratory assessments (serum chemistry, hematology, and urinalysis; see [Section 7.2.2](#) for a complete list of parameters)
 - Archive sample
 - Urine pregnancy test for females of childbearing potential
 - HIV-1 RNA (viral load)
 - HIV-1 viral resistance sample (will be stored for later use if needed)
 - CD4⁺ cell count (within 1 hour before the start of the infusion)

- Immunogenicity of ibalizumab

The patient will also initiate the selected OBR on this day, either at home or in the clinic with site personnel supervision.

After the preceding procedures are completed, site personnel will undertake the following (infusion and post-infusion):

- Administer loading dose of study medication (2,000 mg)
- Record vital sign measurements after the completion of the infusion and observe the patient for at least 1 hour
- Record all AEs

6.3.3 Events for Day 7 (± 1 day)

Day 7 serves as the time point at which the antiviral activity of ibalizumab will be assessed to address the primary effectiveness objective of the study.

Site personnel will undertake the following:

- Assess adherence to the OBR
- Record results of abbreviated physical examination
- Record vital sign measurements, AEs, and concomitant medications
- Collect blood and urine samples for the following:
 - Clinical laboratory assessments (serum chemistry, hematology, and urinalysis; see [Section 7.2.2](#) for a complete list of parameters)
 - Archive sample
 - HIV-1 RNA (viral load)
 - HIV-1 viral resistance sample (will be stored for later use if needed)
 - CD4⁺ cell count

6.3.4 Events for Day 14 (± 1 day), and Weeks 4, 6, 8, 10, 14, 16, 18, 20, 22, 26, 30, 32, 34, 38, 40, 42, 44, 46, 50, 52, 54, 56, 58, 62, 64, 66, 68, 70, 74, 76, 78, 80, 82, 86, 88, 90, 92, 94, 98, 100, 102, 104, 106, 110, 112, 114, 116, 118, 122, 124, 126, 128, 130, 134, 136, 138, 140, and 142 (± 2 days)

The following will be completed before study drug administration:

- Record results of physical examination (complete exam at Week 4 only, abbreviated exam at Weeks 20, 32, and 40 only)
- Record the patient's weight (Weeks 4, 20, 32, and 40 only)
- Record vital sign measurements
- Record AEs and concomitant medications
- Assess adherence to the OBR (Weeks 4, 8, 20, 32, and 40 only)
- Collect urine and perform pregnancy test for females of childbearing potential (Weeks 4, 8, 16, 20, 32, 40, 44, 52, 56, 64, 68, 76, 80, 88, 92, 100, 104, 112, 116, 124, 128, 136, and 140 only)
- Collect blood samples for the following:
 - HIV-1 RNA (viral load) (Day 14, and Weeks 4, 6, 8, 16, and 20 only)
 - HIV-1 viral resistance sample (will be stored for later use if needed) (Day 14, and Weeks 4, 6, 8, 16, and 20 only)
 - CD4⁺ cell count (Day 14, and Weeks 4, 6, 8, 16, and 20 only)

Site personnel will undertake the following after administration of study drug (800 mg):

- Record vital sign measurements after completion of infusion and observe patient for at least 1 hour; if the patient did not experience an AE(s) related to the infusion (local or systemic) through and including the infusion on Day 14, then the observation time can be reduced to 15 minutes
- Record AEs

6.3.5 Events for Weeks 12, 24, 48, 60, 72, 84, 96, 108, 120, 132, and 144/EOS (± 2 days)

Site personnel will undertake the following before administration of study drug:

- Record results of physical examination (complete exam at Week 24, 48, 72, 96, 120, and 144 only ; abbreviated exam at Weeks 12, 60, and 84 only)
- Record the patient's weight (Weeks 12, 24, 48, 60, 72, 84, 96, 120, and 144 only)
- Record vital sign measurements
- Record AEs and concomitant medications
- Assess adherence to the OBR
- Collect blood and/or urine samples for the following:
 - Hepatitis serology and C-reactive protein (Weeks 24, 48, and 96, only)
 - Clinical laboratory assessments (serum chemistry, hematology, and urinalysis; see [Section 7.2.2](#) for a complete list of parameters) (Weeks 12, 24, 48, 60, 72, 84, 96, and 120 only)
 - Archive sample (Weeks 12, 24, 48, 60, 72, 84, 96, 120, and 144 only)
 - Pregnancy test for females of childbearing potential (serum at Weeks 24, 48, 72, and 96 only; urine at all other listed weeks)
 - HIV-1 RNA (viral load)
 - HIV-1 viral resistance sample (will be stored for later use if needed)
 -
 - CD4⁺ cell count (within 1 hour before the start of the infusion)
 - Immunogenicity of ibalizumab (Weeks 24, 48, 72, 96, , 120, and 144 only)

Site personnel will undertake the following after administration of study drug (800 mg):

- Record vital sign measurements after completion of infusion and observe patient for at least 1 hour; if the patient did not experience an AE(s) related to the infusion (local or systemic) through and including the second infusion on Day 14, then the observation time can be reduced to 15 minutes

- Record AEs

6.3.6 Events for Weeks 28 and 36 (± 2 days)

The following will be completed before study drug administration:

- Record the patient's weight (Week 36 only)
- Record vital sign measurements
- Record AEs and concomitant medications
- Collect blood and/or urine samples for the following:
 - Clinical laboratory assessments (serum chemistry, hematology, and urinalysis; see [Section 7.2.2](#) for a complete list of parameters)
 - Archive sample
 - Urine pregnancy test for females of childbearing potential
 - HIV-1 RNA (viral load)
 - HIV-1 viral resistance sample (will be stored for later use if needed)
 - CD4⁺ cell count (within 1 hour before the start of the infusion)

Site personnel will undertake the following after administration of study drug (800 mg):

- Record vital sign measurements after completion of infusion and observe patient for at least 1 hour; if the patient did not experience an AE(s) related to the infusion (local or systemic) through and including the infusion on Day 14, then the observation time can be reduced to 15 minutes
- Record AEs

6.3.7 Events for Week 150/Follow-up Visit (± 2 days) (Study drug is not administered at this visit)

The following procedures will be completed at the Week 102/Follow-up visit:

- Record results of a complete physical examination
- Record the patient's weight
- Record vital sign measurements;
- Record AEs and concomitant medications
- Assess adherence to the OBR
- Collect blood and/or urine samples for the following:
 - Hepatitis serology and C-reactive protein
 - Clinical laboratory assessments (serum chemistry, hematology, and urinalysis; see [Section 7.2.2](#) for a complete list of parameters)
 - Archive sample
 - Urine pregnancy test for females of childbearing potential
 - HIV-1 RNA (viral load)
 - HIV-1 viral resistance sample (will be stored for later use if needed)
 - CD4⁺ cell count
 - Immunogenicity of ibalizumab

6.4 Early Withdrawal Procedures

Patients who withdraw from the study at any time before Week 96/EOS will be asked to complete all Early Withdrawal procedures to ensure safety and collect as much effectiveness data as possible.

The following procedures will be completed at the Early Withdrawal visit (study drug is not administered at Early Withdrawal):

- Record results of a complete physical examination
- Record the patient's weight
- Record vital sign measurements

- Record AEs and concomitant medications
- Assess adherence to the OBR
- Collect blood and/or urine samples for the following:
 - Hepatitis serology and C-reactive protein
 - Clinical laboratory assessments (serum chemistry, hematology, and urinalysis; see [Section 7.2.2](#) for a complete list of parameters)
 - Archive sample
 - Serum pregnancy test for females of childbearing potential
 - HIV-1 RNA (viral load)
 - HIV-1 viral resistance sample (will be stored for later use if needed)
 - CD4⁺ cell count
 - Immunogenicity of ibalizumab

6.5 **Unscheduled Visits**

Unscheduled visits are allowed for the following reasons:

- To perform a confirmatory plasma viral load determination
- To perform confirmatory laboratory testing for clinically abnormal values
- Any time the investigator feels that they are clinically required for safety reasons related to the patient's participation in this trial

Findings during these unscheduled visits must be reported in the EDC system under the unscheduled visit section.

7. Study Assessments

A central laboratory will analyze all blood and urine samples with the exception of the HIV-1 resistance testing and immunogenicity testing, which will be undertaken by appropriate specialty contract laboratories. Urine samples will be analyzed at the site; if abnormal results are obtained for a patient, a urine sample will be sent to the central laboratory for microscopic evaluation.

The following assessments will be conducted at the times indicated in the Schedule of Events (Tables 3-1 through 3-6).

7.1 Activities to Be Completed

7.1.1 Demographic Data, Medical History, and Concomitant Medications

Demographic data, a complete medical history (per patient report), and documentation of prior medications will be collected at Screening; information about recent or concomitant medications will be obtained at each visit. If the patient is enrolling into Cohort 2, the patient will supply official written documentation of HIV-1 infection at Screening, if possible. Otherwise, a sample for an HIV-1 antibody test must be collected as part of the Screening procedures.

7.1.2 Complete Physical Examination

A complete physical examination will include the following organ or body system assessments: head, eyes, ears, nose, throat, musculoskeletal, cardiovascular, lymphatic, respiratory, gastrointestinal, skin, neurological, and other findings of note. Height and weight will be measured at Screening, and weight only will be measured at other times specified.

7.1.3 Abbreviated Physical Examination

An abbreviated physical examination will be limited to lymph nodes, respiratory and cardiovascular systems, abdomen, extremities, and nervous system and assessment of any specific signs and symptoms that the patient reports.

7.1.4 Vital Sign Measurements

Vital sign measurements will include the patient's heart rate (beats/minute taken for 1 full minute), blood pressure (mm Hg), respiratory rate (breaths/minute taken for 1 full minute), and oral temperature (°C). Measurements will be taken within 1 hour before the start of the infusion and 15 minutes after the end of the infusion. Blood pressure and heart rate measurements will be obtained after the patient has been seated for at least 5 minutes. Ideally, each patient's blood pressure should be measured using the same arm and the same size cuff at each visit.

7.2 Blood and Urine Samples

7.2.1 Hepatitis Serology and C-Reactive Protein

Patients will be screened for hepatitis B (surface antigen) and hepatitis C to determine their hepatitis status.

Blood samples will be taken for the analysis of C-reactive protein, which is an inflammatory marker whose concentration increases with acute or chronic inflammation.

7.2.2 Clinical Laboratory Parameters

Collection of blood and urine samples for clinical laboratory assessments will be part of a normal safety profile assessment for the study patients. Patients need not fast before blood sampling. Samples will be processed using standard procedures as described in the laboratory procedures manual and will be analyzed by a central laboratory unless otherwise noted.

The samples will be analyzed for the following:

- **Hematology:** complete white blood cell count with differential, hemoglobin, hematocrit, and platelets
- **Serum chemistry profile:** albumin, alkaline phosphatase, alanine aminotransferase (ALT), amylase, aspartate aminotransferase (AST), blood urea nitrogen, calcium, chloride, creatine phosphokinase, creatinine, direct bilirubin, gamma glutamyl transferase, glucose, lactate dehydrogenase, lipase, lipid profile (total cholesterol, high-density lipoprotein, low-density lipoprotein, and triglycerides), magnesium, phosphorus, potassium, sodium, total bilirubin, total protein, and uric acid
- **Urinalysis:** visual inspection for appearance and dipstick assessment for color, pH, specific gravity, ketones, protein, glucose, bilirubin, nitrite, urobilinogen, and leukocyte esterase

The urinalysis will be performed at the site by qualified personnel. If the results of the urinalysis are abnormal, a urine sample will be sent to the central laboratory for microscopic evaluation. Samples will be processed as described in the laboratory procedures manual before being sent to the central laboratory for evaluation.

Tests with Grade 3 or Grade 4 abnormal results should be repeated within 72 hours of the site becoming aware of the abnormal value(s). See Appendix B for details and definitions of toxicities. The Principal Investigator should discuss any Grade 3 or 4 abnormal laboratory results with the medical monitor/Sponsor for appropriate patient disposition, including potential withdrawal from the study (see [Section 5.3.1](#) for additional information). Per [Section 5.3.1](#), the study treatment should be stopped for all Grade 3 or 4 treatment-related laboratory abnormalities, as defined in Appendix B. Any patient with a Grade 3 or Grade 4 laboratory abnormality that resolves before the next scheduled dose may have the study drug reinstated. If a patient develops a persistent Grade 3 or Grade 4 treatment-emergent laboratory abnormality, excluding triglycerides and cholesterol, that does not resolve prior to the next scheduled study drug administration, study drug may be discontinued. Patients with Grade 3 or 4 triglyceride and/or cholesterol elevations are allowed to continue to receive study drug.

7.2.3 Archive Sample

A separate blood sample will be taken and stored for possible research use.

7.2.4 Serum Follicle-Stimulating Hormone Testing

A serum FSH test will be performed on postmenopausal females at Screening (see [Section 8.7](#)). The level of FSH should exceed 35 IU/L for the patient to be considered postmenopausal. If the patient does not meet this criterion, she must agree to use proper birth control precautions as described in [Section 8.7](#) and must have serum and urine pregnancy tests throughout the protocol at times specified in the Schedule of Events.

7.2.5 Pregnancy Testing

A serum pregnancy test will be performed at Screening, EOS, Early Withdrawal and other defined visits for all females of childbearing potential. A urine pregnancy test will be performed at other defined study visits to confirm that a female has not become pregnant during the study. These tests are performed for the protection and safety of the fetus, as the risk to the fetus is unknown. Any patient who becomes pregnant during the study will be withdrawn from the study. See [Section 8.7](#) for a description of procedures to be followed in case of pregnancy.

7.2.6 HIV-1 RNA Level

Blood samples for viral load will be used to determine the effectiveness of the study regimens and should be drawn before infusion during visits that include an infusion.

7.2.7 HIV-1 Viral Resistance Testing

Blood samples for HIV-1 viral resistance testing should be collected before the start of the infusion at the indicated visits. Viral resistance testing will include assessments of reverse transcriptase, protease, integrase and envelope genes, and chemokine coreceptor utilization; the samples will be collected and stored, and testing will only be performed for patients who experience virologic failure while on the study.

Collected and stored samples may also be used for the Trofile™ Assay, a blood test that identifies the tropism of a patient's HIV strain (i.e., R5, X4, or a combination). The results show whether the patient is infected with the virus that enters cells using the R5 co-receptor, the X4 co-receptor, or both.

7.2.8 CD4⁺ Cell Count

Blood samples for CD4⁺ cell count will be collected over the course of the study to determine how well the immune system is functioning. In most patients infected with HIV, an increase in the number of CD4⁺ cells is an indicator of the effectiveness of antiretroviral medication.

If a patient experiences toxicity, defined as two consecutive laboratory results, at least 14 days apart, with a CD4⁺ cell count below 200 cells/mm³ that also represents a 50% reduction from the baseline CD4⁺ cell count, the patient will be discontinued from the study.

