
Safety and Effectiveness Assessments:
	
Primary safety and effectiveness variables:
 
Cohort 1 and Cohort 2
 
 ■ Safety and tolerability of ibalizumab as assessed by AEs and Discontinuations 
Cohort 2 only
 
 ■ Proportion of patients achieving a $\geq 0.5 \log_{10}$ decrease from Baseline in viral load at Day 7 
Secondary safety and effectiveness variables:
 
Cohort 1 and Cohort 2
 
 ■ HIV-1 sensitivity/susceptibility changes associated with virologic failure after administration of ibalizumab 
Cohort 2 only
 
 ■ Proportion of patients with HIV-1 RNA levels < 50 copies/mL and < 400 copies/mL at assessment time points ■ Mean change from Baseline in viral load at Day 7 and all assessment time points ■ Proportion of patients achieving a $\geq 0.5 \log_{10}$ and $\geq 1.0 \log_{10}$ decrease from Baseline in viral load at all assessment time points

Safety Assessments:
	
Safety assessments will include the following:
 
 ■ Physical examinations ■ Vital sign measurements ■ Clinical laboratory parameters (hematology, serum chemistry, and urinalysis) ■ Monitoring of AEs and concomitant medications ■ Incidence of Class C events as defined by the CDC Classification System for HIV Infection (Appendix A) ■ Anti-ibalizumab antibody levels (immunogenicity of ibalizumab)

Statistical Considerations:	
Sample Size: A sample size of approximately 100 patients is anticipated to be enrolled, though the number of participating patients will not be limited and may exceed 100. The analysis of study data will be primarily descriptive, with emphasis on tabular and graphical displays. Summary descriptive statistics will be calculated along with point and interval estimates of AEs.
 
Effectiveness: (Cohort 2 only) The primary effectiveness endpoint of the study is the proportion of patients achieving a $\geq 0.5 \log_{10}$ decrease from Baseline in viral load at Day 7.
 
Safety Analyses: The safety analyses will include descriptions of treatment-emergent AEs (TEAEs), Class C events per the CDC Classification System for HIV Infection, clinical laboratory test results, physical examination findings, vital sign results, and immunogenicity of ibalizumab.

------------------------------------	---

ABBREVIATIONS

ABBREVIATION	TERM
AE	adverse event

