3.1 Overall Design

This Phase 3, multicenter, expanded access study will evaluate the safety and tolerability of ibalizumab in treatment-experienced patients infected with MDR HIV-1. Eligible patients will include (1) those currently receiving ibalizumab under a TaiMed-sponsored or Investigator-sponsored IND protocol and (2) treatment-experienced patients with no history of ibalizumab treatment who are on a failing regimen, or who have failed and are off treatment.

Patients will be enrolled in one of two Cohorts (Cohort 1 and Cohort 2):

Cohort 1 (continuing treatment)

- Patients will continue on an ibalizumab containing regimen at their current dosage in combination with a current OBR.

Cohort 2 (initiating ibalizumab)

- On Day 0/Baseline, patients will receive one 2,000 mg dose (loading dose) of ibalizumab. The OBR will be initiated on Day 0/Baseline and must include at least one agent to which the patient's virus is susceptible.
- Beginning at Day 14, an 800 mg of ibalizumab will be administered every 2 weeks through the remainder of the study.

Virologic failure is defined as two consecutive measurements at Week 24 or later if less than a 0.5 log₁₀ decline from the Baseline viral load (see Section 9.4 for the definition of Baseline).

Patients will be discontinued from the study at the patient's request or if the patient becomes pregnant, at investigator request, for protocol violation, for virologic failure, for treatment-related serious or intolerable AE(s) (Division of AIDS [DAIDS] criteria, see Appendix B), or for toxicity (defined as two consecutive laboratory results, at least 14 days apart, with a CD4⁺ cell count below 200 cells/mm³ that also represents a 50% reduction from the Baseline CD4⁺ cell count).

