5.3 Patient Withdrawal and Discontinuation

5.3.1 Reasons for Withdrawal

A patient may be withdrawn from the study if the patient:

- Withdraws consent to participate or requests an early discontinuation at any time during the study
- Is in violation of the protocol
- Becomes pregnant during the study (see [Section 8.7](#) for a description of procedures to be followed in case of pregnancy)
- Experiences virologic failure
- Experiences a treatment-related serious or intolerable AE(s) (according to DAIDS criteria, see Appendix B)
- Experiences toxicity, defined as two consecutive laboratory results, at least 14 days apart, with a CD4⁺ cell count below 200 cells/mm³ that also represents a 50% reduction from the baseline CD4⁺ cell count

The study treatment should be discontinued for all Grade 3 or 4 treatment-related abnormalities, as defined in Appendix B. Treatment-emergent Grade 3 or Grade 4 lab abnormalities should be retested within 72 hours. Any patient with a Grade 3 or Grade 4 lab abnormality that resolves before the next scheduled dose may have the study drug reinstated. If a patient develops a persistent Grade 3 or Grade 4 treatment-emergent laboratory abnormality, excluding triglycerides and cholesterol, that does not resolve prior to the next scheduled study drug administration, study drug may be discontinued.

A patient experiencing one or more treatment-emergent SAEs will receive treatment and follow-up evaluations by the Principal Investigator, or they will be referred to another appropriate physician for treatment and follow-up. Withdrawal from the study will be at the discretion of the Principal Investigator/Sponsor.

The investigator will also withdraw a patient if the Sponsor or local regulatory agency (e.g., FDA) terminates the study. Upon occurrence of an SAE, the Principal Investigator will notify the Sponsor or designee of these events via the SAE hotline. If a patient is discontinued because of an AE, the

event will be followed until satisfactory resolution or until the Principal Investigator deems the event to be chronic or the patient to be stable.

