For Cohort 2, patients will complete all screening procedures during the six weeks before Baseline/Day 0. Successful screening results will allow the patients to proceed to the Baseline/ Day 0 Visit, where they will initiate the selected OBR in addition to undergoing physical and laboratory measures. At this visit patients will also receive the loading dose of the study medication (2000 mg). Patients will return to the clinic on Day 7 for effectiveness and safety evaluations, and on Day 14 and every two weeks thereafter through the remainder of participation in the study (up to 144 weeks) for study drug administration (800 mg) and effectiveness and safety evaluations. Patients who are discontinued or who withdraw from the study prematurely will be asked to return for an Early Withdrawal visit to have all assessments detailed in the Schedule of Events for that visit performed.

All patients who complete Week 144 or end of study (EOS) visit will return for a follow-up visit at Week 150. Patients may be discontinued from the study at the patient's request or if the patient becomes pregnant, at investigator request, for a protocol violation, for treatment-related serious or intolerable adverse events (AEs), for toxicity (defined as two consecutive laboratory results, at least 14 days apart, with a CD4+ T-cell count below 200 cells/mm3 that also represents a 50% reduction from the Baseline CD4+ T-cell count), or for virologic failure. Virologic failure is defined as two consecutive measurements beginning at Week 24 or later if less than a 0.5 log10 decline from the Baseline viral load.

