## 4.5.2.3 Virologic Outcome

## Snapshot Approach

Virologic outcome will be assigned for each patient at each key visit after Week 12 [Weeks 24, 48, 72, 96, 120, and 144/EOS], per the snapshot approach, using the following standard categories:

- 1=Virologic success (≥0.5 log10 decline from Baseline in viral load)
- 2a=(<0.5 log10 copies/mL drop from Baseline in viral load)
- 2b=Discontinued efficacy portion of study because of virologic failure (may still continue safety)
- 2c=Discontinued because of other reasons and the drop from baseline in viral load at the time of discontinuation was <0.5 log10 copies/mL
- 2d=OBR changed
- 3a=Discontinued because of AE or death
- 3b=Discontinued because of other reasons and the drop from baseline in viral load at the time of discontinuation was >=0.5 log10 copies/mL
- 3c=Missing data during the window but on study

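### Meeting the CD4 toxicity or virologic failure criterion means discontinuation in some sections and only possible discontinuation in others, so the discontinuation count depends on which section a site follows

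*Protocol*

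**What the plan says.** **CD4 toxicity.** The definition is the same throughout: two successive counts, 14 or more days apart, under 200 cells/mm³ and down by half from baseline. Its consequence is not the same. Protocol Section 7.2.8 ends with "that also represents a 50% reduction from the baseline CD4⁺ cell count, the patient will be discontinued from the study". Section 3.1 opens its list of grounds with "Patients will be discontinued from the study at the patient's request" and includes CD4 toxicity in the same sentence. Section 5.3.1 opens the corresponding list with "A patient may be withdrawn from the study if the patient", and SAP Section 2.1 with "Patients may be discontinued from the study at the patient's request". The Protocol Summary, under Study Design, also uses *may*.

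**Virologic failure.** It stands in the same lists with the same opening verbs. Protocol Section 3.2 also names it, once for each group of patients, among the events at which treatment ends. The SAP's snapshot categories (Section 4.5.2.3) define code 2b as "Discontinued efficacy portion of study because of virologic failure (may still continue safety".

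**Role of discontinuation.** The Protocol Summary gives as a primary variable for both cohorts "Safety and tolerability of ibalizumab as assessed by AEs and Discontinuations". Section 3.2 repeats this role. Protocol Section 9.3 and SAP Section 4.1 tabulate the counts and reasons.

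**Laboratory toxicity (a secondary point).** Section 5.3.1 says "The study treatment should be discontinued for all Grade 3 or 4 treatment-related abnormalities, as defined in Appendix B", and Section 7.2.2 repeats the rule for laboratory values. Section 7.2.2 also says "Patients with Grade 3 or 4 triglyceride and/or cholesterol elevations are allowed to continue to receive study drug".

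**The concern.** Two sites with identical patients could act differently and each be following the protocol. One stops a patient who meets the CD4 criterion under Section 7.2.8. The other keeps such a patient under Section 5.3.1. About 40 sites (Protocol Summary) or 50 sites (SAP Section 3.1) are expected. The discontinuation rate would then reflect partly how each site read the protocol and partly how patients fared.

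The ambiguity also reaches protocol violations. Section 11.5 counts it as a violation to keep on study a patient whose withdrawal is required. Whether withdrawal is required is exactly what the sections disagree on. The same decision is a violation under Sections 3.1 and 7.2.8 and compliant under Section 5.3.1.

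**Working it through.** The check compares wording. No sample-size or precision figure in the plan bears on it, and there is no plan figure to reproduce.

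**Step 1: the consequence stated in each place.**

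| Place | CD4 toxicity | Virologic failure |
|---|---|---|
| Protocol Summary, Study Design | may | may |
| Protocol 3.1 | will | will |
| Protocol 3.2 | not named | end of treatment |
| Protocol 5.3.1 | may | may |
| Protocol 7.2.8 | will | not covered |
| SAP 2.1 | may | may |
| SAP 4.5.2.3, code 2b | not covered | leaves an efficacy portion, may stay for safety |
| SAP Section 6, virologic outcome listing footnote, code 2b | not covered | discontinued |

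Section 3.2 speaks of treatment-limiting toxicity without saying whether the CD4 criterion counts as such.

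**Step 2: could *may* and *will* be loose synonyms?** Not on the protocol's own usage. For missed doses, Section 4.4.1 uses *may* for withdrawal in Cohort 1 and Section 4.4.2 uses *will* in Cohort 2, so the two words carry different force.

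**Step 3: could one section govern?** Neither document gives an order of precedence.
- Section 5.3.1 cannot simply prevail. Its *may* list includes pregnancy, for which Sections 7.2.5 and 8.7 make withdrawal mandatory.
- Treating 7.2.8 as the specific rule and 3.1 as a general summary does not help, because 3.1 also says *will* for the whole list.

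**Step 4: code 2b.** The protocol has no separate efficacy portion that a patient can leave while staying on for safety. The SAP's own listing footnote for the same code omits that idea, so the SAP also disagrees with itself.

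**Step 5: size per patient.** If k patients meet a criterion and are kept where another reading would stop them, the overall discontinuation rate changes by k/N. With N of about 100 (Protocol Summary; SAP Section 3.1) and k = 1, the change is 1/100 = 1 percentage point. SAP Section 3.4.1 also displays results by patient group. In a group of n patients the change is 1/n, which is larger because n is below N. The documents give no expected k.

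**Step 6: the Grade 3/4 laboratory sentences.** Sections 5.3.1 and 7.2.2 each contain three statements: stop for all treatment-related Grade 3/4 abnormalities; drug may be reinstated if the abnormality resolves before the next dose; drug may be discontinued if a treatment-emergent abnormality other than triglycerides or cholesterol persists. Section 7.2.2 adds the lipid allowance. The text does not say how these fit together for an abnormality that is both treatment-related and persistent, or for a lipid elevation judged treatment-related.

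**The case against.** The strongest reply accepts the wording clash and disputes its consequences.

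- **The analysis is partly protected.** The study is single-arm and descriptive with no formal hypothesis test planned (SAP Section 3.4.2). SAP Section 3.3.4 sets all visits after confirmed virologic failure to failure whether or not the patient stops, which largely shields the viral load results. Reasons for stopping are tabulated, and events leading to discontinuation have their own tables. This stands for efficacy and for separating reasons. It does not protect the count itself, because a patient who is kept on contributes no discontinuation and no reason.
- **Section 11.5 has an exception route.** An investigator may ask the medical monitor in writing to keep a patient, and the violations listing shows approval and date. This makes recorded cases reviewable. It applies only where the protocol requires discontinuation, so it does not settle whether it does.
- **A reader might infer that nothing planned distinguishes meeting a criterion from being stopped.** The documents do not support that. CD4 toxicity is flagged by patient and visit in Listing 16.2.6.2, a Study Discontinuation listing is planned, and the snapshot table separates codes 2a and 2b. The comparison can be made patient by patient; only a summary table is missing.
- **A reader might infer that Grade 3/4 abnormalities show the same contradiction.** They do not. The strong verb there is *should*, the paragraph can be read as stop, retest, then reinstate or discontinue, and the lipid sentence can be read as a specific exception. It is unclear drafting about study drug, whereas the other two criteria concern study participation.
- **A reader might take the low baseline CD4 counts in TMB-301 (median 73 cells/mm³) as a sign of a large effect.** That figure bears on where the trigger lies, not on how often it is met or what differs between the two wordings. The mean CD4 changes that the protocol reports from the Phase 2b study and TMB-301 are increases.

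**Conclusion.** The consequence of CD4 toxicity and of virologic failure is contradictory within the protocol and between the protocol and the SAP, and nothing in either document resolves it. The number of discontinuations, and the number of violations for keeping a patient who had to withdraw, depend on which section a site follows. The effect is about 1 percentage point on the overall rate per patient handled differently, assuming about 100 patients. The total cannot be estimated because no rate is given for either criterion. The Grade 3/4 sentences need clarifying but are a lesser matter. No view is taken here on which consequence is clinically right.

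**What to change.** 1. Give each of the two criteria one consequence, chosen by the sponsor's medical team, and state it identically in the Protocol Summary, Protocol Sections 3.1, 3.2, 5.3.1 and (for CD4) 7.2.8, and SAP Section 2.1.
2. Align SAP code 2b in Section 4.5.2.3 with the protocol and with the listing footnote in SAP Section 6.
3. In Protocol Sections 5.3.1 and 7.2.2, state how the rule for treatment-related Grade 3/4 laboratory abnormalities relates to the reinstatement sentence, the sentence on persistent abnormalities and the lipid allowance.
4. In SAP Section 4.1, add a table of patients who met the CD4 toxicity criterion and patients who met the virologic failure criterion, each split by discontinued or not. Derive it from observed values: SAP Section 3.3.4 replaces a missing viral load with the baseline value, which would itself count as less than a 0.5 log₁₀ decline.

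The cost is consistent wording in one amendment and one extra table from viral load, CD4 and disposition data already collected. A Grade 3/4 row is not proposed. SAP Section 4.3.3 plans normal-range flags rather than toxicity grades, and relatedness is recorded for adverse events, so that row would not come readily from the planned data.
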